#### 9.7.1.1

#### Analysis Subgroups

The analysis of the primary and secondary outcomes will be performed among the following subgroups of the most recent DMT taken prior to initiation with cladribine tablets. A non-exhaustive list of such regulatory approved DMTs by subgroup is provided in [Table 2](#).

**Table 2** Subgroups by Most Recent prior disease-modifying therapy

Previous disease-modifying therapy class	Therapies
Naïve to disease-modifying therapies	-
Prior platform therapy	Interferon beta; teriflunomide; dimethyl fumarate; glatiramer acetate
Prior high-efficacy cell-depleting treatment	Alemtuzumab; ocrelizumab
Prior high-efficacy non-depleting treatment	Natalizumab; fingolimod

Patients will be classified in only one of the subgroups. For patients who have taken more than one prior DMT, the drug which was taken most recently prior to treatment initiation with cladribine tablets (i.e., the last prior DMT) will be used for categorisation. Patients who had a gap period between the most recent prior DMT and the initiation with cladribine tablets will be classified in the subgroup according to their last prior therapy.

The medications will be coded using WHO Drug Dictionary. A list of the medication codes that qualify for enrolment in each subgroup will be provided in the IAP.

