8.2 Subgroup Definition and Parameterization

Subgroup analyses will be performed on primary and secondary outcomes. All subgroup analyses will be exploratory, no adjustment for multiplicity will be performed.

The following subgroups will be defined:

Most recent prior disease-modifying therapy:

- Naïve to disease-modifying therapies
- Prior platform therapy
- Prior high-efficacy cell-depleting treatment
- Prior high-efficacy non-depleting treatment

Prior and subsequent disease-modifying therapies will be medically reviewed on an ongoing basis and classified by the medical advisor. This process will be described in a separate document. DMTs classes will be linked with electronic case report form (eCRF) data for data analysis.

9 General Specifications for Data Analyses

Index date

Cladribine initiation date will be used as an index date to determine baseline and on-treatment periods.

Initial date

According to the protocol, data will be collected counting from 1 year prior to cladribine initiation date. The initial date will be calculated as follows:

- Initial date: Index date/cladribine initiation date - 1 (year).

All assessments occurred from initial date onwards will be considered for the analysis.

Pre-treatment period is defined as follows:

- Pre-treatment: from initial date until cladribine initiation date - 1 (day).

Listings

In the individual participant data listing all individual data will be listed as measured. Repeated measurements will be included in the listings. All listings will be sorted by subject ID, study period, and date of assessment as appropriate.

Tables and Descriptive Statistics

All data will be summarised by the most recent prior DMT group and overall. Repeated measurements (in the same time window) included in the listings will not be used for statistical analyses or summaries unless the repeated measurement was performed due to unreliable values/technical reasons.

Unless otherwise specified, continuous variables will be summarised using descriptive statistics, i.e. the number of participants with non-missing values (n), the number of participants with missing values, (nmiss), mean, standard deviation (SD), median, 25th percentile (Q1) and 75th percentile (Q3), minimum, and maximum. If there are no missing values, the number of participants with missing values should be indicated by a 0.

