Adverse events	Incomplete AE-related dates will be imputed as follows: 
• In case the onset date is partially missing but the onset month and year, or the onset year are equal to cladribine initiation then the onset date will be imputed by the minimum of cladribine initiation date and AE resolution date (if not missing).• In all other cases, the missing onset day or missing onset month will be imputed by 1.• Incomplete stop dates will be imputed by the last day of the month (if day is missing only), if not resulting in a date later than the date of participant's death. In the latter case, the date of death will be used to impute the incomplete stop date.• In all other cases, the incomplete stop date will not be imputed.
Previous and concomitant medication (including prior/subsequent DMTs)	Incomplete prior/concomitant medication (and DMT) start and stop dates will be imputed as follows: 
• If the medication start date is missing completely, then the medication start date will be replaced by the cladribine initiation date.• If the day of medication start date is missing, but the month and year are equal to the cladribine initiation date, then the medication start date will be replaced by the cladribine initiation date. For example, if the medication start date is --/JAN/2015, and cladribine initiation date is 15/JAN/2015, then the imputed medication start date will be 15/JAN/2015.• If both the day and month of medication start date are missing but the start year is equal to the cladribine initiation date, then the medication start date will be replaced by the cladribine initiation date. For example, if the medication start date is --/---/2014, and cladribine initiation date is

	
19/NOV/2014, then the imputed medication start date will be 19/NOV/2014.
 
• In all other cases the missing medication day or missing medication month will be replaced by 1. Incomplete stop date will be replaced by the last day of the month (if day is missing only), if not resulting in a date later than the date of participant's death. In the latter case the date of death will be used to impute the incomplete stop date.• In all other cases the incomplete medication stop date will not be imputed. 
In case an imputed medication start date is later than the medication stop date, it will be replaced by the medication stop date.

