11.2 Medical History and Comorbidities

Medical history and comorbidities (past and ongoing) will be presented for the FAS. It will be categorized as follows:

- Past medical history and comorbidities: any disease resolved during the pre-treatment period defined in [Section 9](#) (year prior to cladribine initiation).
- Ongoing comorbidities: any disease that started or is ongoing at cladribine initiation

Any disease that was resolved more than one year prior to cladribine initiation is not relevant will not be included in the analysis.

Medical history and comorbidities will be summarised from the “Medical History and comorbidities” eCRF page, using the most recent Medical Dictionary for Regulatory Activities (MedDRA) version at the time of database lock, preferred term (PT) as event category and system

organ class (SOC) body term as body system category. Each participant will be counted only once within each PT or SOC.

12 Previous or Concomitant Therapies/Procedures

Medications will be presented for the FAS by the most recent prior DMT and overall. Previous and concomitant medications will be presented in separate tables and are defined as follows:

- Previous medications are defined as any medication discontinued during the year prior to cladribine initiation.
- Concomitant medications are defined as any medication taken during the course of the study, with a starting date greater than or equal to the administration of cladribine , or with a starting date prior to the administration of cladribine and ongoing at the time of the administration of cladribine .

The World Health Organization Drug dictionary (WHO-DD) will be used for coding of prior and concomitant medications and they will be described using PT as applicable. The most recent version of WHO-DD available at the time of data-cut will be used for medications coding.

Previous and concomitant medications will be listed. Concomitant procedures, if any, will also be listed.

13 Exposure

The following analyses will be performed based on the FAS by the most recent prior DMT and overall.

All calculations and summaries for treatment in Year 1 and Year 2 of cladribine will be based on “Treatment with cladribine Tablets” eCRF page. For additional courses of cladribine (Year 3, Year 4, Year 5 data will be pulled from the “Prior and Subsequent Disease Modifying Therapy” eCRF page if the treatment reported is “cladribine”.

The summary of cladribine exposure will include the following information:

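### SAP 9.10 can date a DMT that ended before cladribine as starting with it, and the SAP does not say whether imputed dates set the most-recent-prior-DMT subgroup

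*SAP*

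**What the plan says.** One row of the date table in SAP 9.10 covers previous and concomitant medication and expressly includes prior and subsequent DMTs.

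- **Start dates.** "If the medication start date is missing completely, then the medication start date will be replaced by the cladribine initiation date". The initiation date is also used when only the day is missing and the month and year match cladribine; in the SAP's example, "then the imputed medication start date will be 15/JAN/2015". The same applies to year-only starts in the cladribine year: "If both the day and month of medication start date are missing but the start year is equal to the cladribine initiation date". Any other missing day or month becomes 1.
- **Stop dates.** "Incomplete stop date will be replaced by the last day of the month (if day is missing only"), limited only by the date of death. For everything else, "In all other cases the incomplete medication stop date will not be imputed".
- **Guard.** An imputed start that falls after the stop is reset to the stop.

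SAP 12 defines as concomitant any medication "with a starting date greater than or equal to the administration of cladribine", or one begun earlier and still ongoing at that point. Previous medication must have been discontinued in the year before initiation.

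For the subgroups, protocol 9.7.1.1 states that "the drug which was taken most recently prior to treatment initiation with cladribine tablets (i.e., the last prior DMT) will be used for categorisation", whatever the gap before cladribine. SAP 8.2 has the medical advisor review and classify prior and subsequent DMTs under a separate document, after which "DMTs classes will be linked with electronic case report form (eCRF) data for data analysis".

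**The concern.** Setting an unknown start to the initiation date is a common, cautious default for concomitant drugs. For a prior DMT it works the wrong way: it moves a piece of pre-treatment history to the one date that separates prior from subsequent. The guard should prevent this, but it needs a usable stop date, and the stop rule withholds one exactly where the chart gives only a year. A recorded year that proves the drug ended before cladribine is then ignored.

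The same table treats the other item of pre-treatment history differently. A year-only MS diagnosis date in the cladribine year goes to 1 January, and a wholly missing one is not imputed.

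The most recent prior DMT defines the four subgroups in which every primary and secondary outcome is reported. Partial dates are foreseeable, because protocol 9.3 collects DMTs from charts back to the initial MS diagnosis.

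**Working it through.** **Step 1: reproduce the SAP's own examples.** Applied literally, the rules turn a start of --/JAN/2015 with cladribine on 15/JAN/2015 into 15/JAN/2015. They turn --/---/2014 with cladribine on 19/NOV/2014 into 19/NOV/2014. Both agree with SAP 9.10.

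**Step 2: single records.** Assume cladribine on 10/SEP/2018 and a drug that truly ended before then.

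| Recorded start | Recorded stop | Imputed start | Imputed stop | Result |
|---|---|---|---|---|
| missing | 2014 | 10/SEP/2018 | missing | looks started with cladribine and ongoing |
| 2018 | 2018 | 10/SEP/2018 | missing | same |
| 10/MAR/2016 | --/SEP/2018 | 10/MAR/2016 | 30/SEP/2018 | false overlap; the start is still prior |
| missing | --/MAY/2014 | 31/MAY/2014 | 31/MAY/2014 | guard works; stays prior |

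Under SAP 12, rows 1 and 2 are concomitant because a start equal to initiation counts. Row 3 is concomitant because the drug looks ongoing. The drug in row 1 ended in 2014 and belongs in neither SAP 12 table.

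**Step 3: which combinations fail.** Five invented histories, each fully stopped before 10/SEP/2018, were crossed with four levels of completeness for the start and four for the stop: 5 × 4 × 4 = 80 patterns.

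| Stop date recorded as | Patterns | Start or stop on or after initiation |
|---|---|---|
| complete | 20 | 0 |
| day missing | 20 | 8 (all with the stop in the cladribine month) |
| year only | 20 | 7 |
| missing | 20 | 7 |
| total | 80 | 22 |

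In 17 patterns the start lands on initiation, in 8 the stop lands after it, and in 3 both happen: 17 + 8 − 3 = 22. No start moves past initiation; only stops do. The grid shows where the rule fails. It does not estimate how often.

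**Step 4: from date to subgroup.** Suppose imputed dates set the order, and prior means a start before initiation, consistent with SAP 12 counting equality as concomitant.

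- If the affected drug is the only prior DMT, the patient looks DMT-naïve.
- If it is the true last DMT and an older one has usable dates, the patient falls back to the older one.
- A truly subsequent DMT with a missing start receives the same date, so the imputed date cannot tell the two apart.

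**Step 5: overall rate.** DMT dates could reach the overall annualised relapse rate only through the date of last contact (SAP 9.5). That section admits imputed dates only when just the day was missing. A stop moved to the end of the cladribine month is not the latest contact for a patient who completed both Year 1 treatment weeks, as eligibility requires. The overall estimate is unchanged.

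**Step 6: illustrative size.** None of these inputs is in the documents. If 70 of the minimum 90 patients were pre-treated and 2% to 5% had such records, 0.02 × 70 = 1.4 to 0.05 × 70 = 3.5 patients would be affected. Take a subgroup of 10 with 1 relapse in a full person-year each (1/10 = 0.10) and add one misplaced patient:

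- no relapse: 1/11 = 0.091
- the protocol's expected rate of 0.14: 1.14/11 = 0.104
- one relapse: 2/11 = 0.182

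**The case against.** The strongest reply is that no text makes imputed dates drive the subgroup. SAP 8.2 gives prior and subsequent DMTs to the medical advisor under a document not available here. Protocol 9.3 and Table 1 collect prior and subsequent DMTs as separate items, with prior ones only at the first chart review, and the eCRF page may carry a status field. Protocol 9.7.1.1 speaks of the drug actually taken last. This stands: a reader might infer that patients will be placed in the wrong subgroup, and the documents do not establish that. They establish silence about the source of the flag. SAP 8.2 links drug classes to eCRF data; it does not say whether order in time comes from the review, the recorded dates or the imputed dates. If the review does override the dates, the subgroups can be right while the SAP 12 tables contradict them.

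Three limits also stand. First, the failing combinations are narrow, and the guard protects the better-documented records. Second, the false overlap from a day-missing stop does not by itself change the subgroup when the start is known. A reader might also see in it a breach of the monotherapy criterion, but eligibility is judged from the chart, and an imputed analysis date cannot breach it. Third, the subgroups are exploratory and no hypothesis is tested.

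**Conclusion.** The date rule is defective as written for prior DMTs with a year-only or missing stop combined with a missing start or a year-only start in the cladribine year. It is also defective for day-missing stops in the cladribine month. The direct result is a wrong imputed date and, under SAP 12, a drug wrongly counted as concomitant.

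Subgroup misclassification is conditional on imputed dates setting the order. If they do, the by-subgroup primary and secondary results are exposed. The size cannot be computed, because the documents give no rate of partial DMT dates; on the assumptions in the working it is a few patients. A reader might take 22 of 80 as a frequency or 0.10 to 0.182 as the expected shift. The first is a constructed grid, and the second requires the misplaced patient to relapse in that year. The point merits correction because the rule is explicit and the repair is cheap, not because the headline result is in doubt.

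**What to change.** Amend SAP 8.2 and 9.10 as follows.

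1. Derive prior/subsequent status and the most-recent-prior-DMT flag from recorded data and the medical review, before any date imputation. Lock both before database lock and build the subgroups from them.
2. For DMTs flagged prior, treat a year-only stop as an upper bound of 31 December of that year, and cap every imputed stop at the day before initiation. Never impute a start after that bound, and do not apply the default to the initiation date. In the examples above, a 2014 stop gives a bound of 31/DEC/2014, and --/SEP/2018 gives the earlier of 30/SEP/2018 and 09/SEP/2018, that is 09/SEP/2018.
3. Send DMTs with year-only dates in the initiation year and no recorded status to the medical review; do not assign them automatically.

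The cap must not be applied to all DMTs. With cladribine on 15/JAN/2018 and a truly subsequent DMT recorded only as 2018 for both start and stop, a general cap would set the stop to 14/JAN/2018 and make the drug prior.

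The cost is SAP wording, two locked flags and a small addition to a medical review that already takes place. No new data are needed.

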### 7.2

### Mavenclad® (Cladribine Tablets)

Over recent years, there has been an increase in the number of available disease-modifying therapies (DMT) for treatment of MS (Wingerchuk 2014). Despite the recent approvals of such therapies, the treatment burden of MS remains significant. New treatment options are still required to reduce the number of relapses and disease progression that patients experience (Hadjigeorgiou 2013, Tramacere 2015, Tsivgoulis 2015, Lucchetta 2020).

Mavenclad® (cladribine tablets) is approved (European Medicines Agency approval on 25 August 2017) for the treatment of highly-active relapsing MS in adults. These tablets involve a synthetic deoxyadenosine analogue that acts in peripheral tissues and enters the CNS, where it is taken up by lymphocytes and phosphorylated by deoxycytidine kinase. This results in targeted and sustained reductions of the T and B lymphocytes that are implicated in the pathogenesis of MS (Leist 2011).

It has been demonstrated that treatment with cladribine tablets in 2 short courses over 2 consecutive years has consistently shown robust clinically and statistically significant benefits in patients across the spectrum of relapsing MS (early to late stages, treatment naïve or experienced patients) (Giovannoni 2010, Leist 2011). The recommended cumulative dose of cladribine tablets is 3.5 mg/kg body weight over 2 years, administered as 1 treatment course of 1.75 mg/kg per year. Each treatment course consists of 2 treatment weeks, one at the beginning of the first month and one at the beginning of the second month of the respective year. Detailed information on the chemistry, pharmacology, efficacy, and safety of cladribine tablets is provided in the Summary of Product Characteristics (SmPC). Overall, the most common, clinically relevant adverse reactions

reported among patients treated with cladribine tablets in clinical studies are lymphopenia and herpes zoster.

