## 9.2.2 Definition of Study Cohorts and Description of Treatments

This is a multicentre chart review study enrolling subjects with HDA-RRMS, who completed at least Year 1 treatment with cladribine tablets in routine clinical practice following the SmPC.

According to the EU SmPC, each treatment year consists of 2 treatment weeks, 1 at the beginning of the first month and 1 at the beginning of the second month of the respective treatment year. Each treatment week consists of 4 or 5 days on which a subject receives 10 mg or 20 mg (1 or 2 tablets) as a single daily dose, depending on body weight. If necessary, the treatment course in Year 2 can be delayed for up to 6 months (18 months after initiation) to allow for recovery of lymphocytes (at least 800 cells/mm^3). If this recovery takes more than 6 months, the subject should not receive cladribine tablets anymore.

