9.2 Study Day

Day 1 is the day of cladribine initiation date (i.e. index date), the day before is Day -1 (no Day 0 is defined). Study day is defined relative to Day 1.

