Dates of cladribine	
Start date of cladribine :
 
• If the day is missing and the month and year are available, the missing day will be imputed to the 15th of the month.• If both the month and day are missing and the year is available, and the end date is available for cladribine treatment Year 1 Week 2, cladribine initiation date will be imputed to the first day of the month prior to the date of Year 1 Week 2. For example, if the end date of week 2 is --/FEB/2019, the cladribine initiation date will be 01/JAN/2019. 
End date of cladribine :
 
• If the last date of cladribine is completely missing and no death date the participant should be considered to be ongoing and use the cut-off date for the analysis as the last dosing date• If the last date of cladribine is partially missing, then imputed last dose date is: = Last day of the month, if both Year and Month are available and Year = Year of min (discontinuation date, death date) and Month < the month of min (discontinuation date, death date)

10 Study Participants

The subsections in this section include specifications for reporting participant disposition and study discontinuations. Additionally, procedures for reporting protocol deviations are provided.

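### The rules for a partial cladribine start date ignore recorded Week 1 and Week 2 dates, so the index date can fall after Week 1 has ended or weeks before the first dose

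*SAP*

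**What the plan says.** SAP 9.10 (Dates of cladribine) has two rules for a partial start date.

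- Day missing: "If the day is missing and the month and year are available, the missing day will be imputed to the 15th of the month". No condition refers to any other course date.
- Day and month missing, year known, Year 1 Week 2 end date available: "cladribine initiation date will be imputed to the first day of the month prior to the date of Year 1 Week 2". The SAP illustrates: "For example, if the end date of week 2 is --/FEB/2019, the cladribine initiation date will be 01/JAN/2019".

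For previous and concomitant medication, including other DMTs, the same section adds a guard: "In case an imputed medication start date is later than the medication stop date, it will be replaced by the medication stop date". The cladribine rules have none.

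SAP Section 9 gives this date its role: "Cladribine initiation date will be used as an index date to determine baseline and on-treatment periods". SAP 9.2 makes it Day 1. From it are counted the relapse years and the 84-day (or 56-day) induction cut (9.6), the 60-day baseline look-back (9.1) and the on-treatment periods (9.7). The full treatment period in turn defines TEAEs (15.1).

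On dosing, Protocol 7.2 says "Each treatment course consists of 2 treatment weeks, one at the beginning of the first month and one at the beginning of the second month", and Protocol 9.2.2 says "Each treatment week consists of 4 or 5 days". Protocol 9.2.1.1 admits only initiations on or after 22 August 2017.

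**The concern.** An imputed start date can contradict dosing dates in the same record. If the start is --/JAN/2019 and Week 1 ended on 06/JAN/2019, the index date becomes 15/JAN/2019, nine days after the week it is meant to open. A start known only as August 2017 becomes 15/AUG/2017, before the earliest eligible date.

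The consequences depend on direction.

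- **Index too late.** A fully dated adverse event between the first dose and the imputed index has its onset before the full treatment period and drops out of the TEAE tables. A lymphocyte count taken after dosing began can be selected as baseline.
- **Index too early.** A relapse shortly before true initiation moves out of Year -1 into Days 1-83. The main Year 1 analysis excludes those days, so the relapse counts in neither year. A pre-dose EDSS score or lymphocyte count taken after the imputed index becomes post-baseline.

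**Working it through.** **Inputs.** Both rules and the worked example: SAP 9.10. Week length of 4 or 5 days: Protocol 9.2.2. Weeks about one month apart: Protocol 7.2. Induction 84 days and baseline look-back 60 days: SAP 9.6 and 9.1. Expected ARR 0.14 and confidence interval half-width 0.072: Protocol 9.5.

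**Assumptions.** True start dates evenly spread over 1 September 2017 to 31 August 2020 (1,096 days); Week 2 starting 28, 30 or 35 days after Week 1.

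**The SAP's own example.** Week 2 end in February 2019; first day of the preceding month = 01/JAN/2019. Reproduced.

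**Missing day.** Error = 15 - true day of month.

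- True day 1: 15 - 1 = 14 days late. True day 31: 15 - 31 = 16 days early.
- Mean absolute error 7.6 days; mean signed error -0.7 days, so the rule is nearly centred.
- A 5-day Week 1 starting on day d ends on d + 4. The 15th falls later if d + 4 < 15, so d is 1 to 10: 360/1,096 = 33%.
- A 4-day week ends on d + 3, so d is 1 to 11: 396/1,096 = 36%.

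**Missing day and month.** Error = first of the month before the Week 2 end date, minus true start. With 5-day weeks, Week 2 end = start + spacing + 4.

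| Spacing | Mean error (days) | Range (days) | At least 14 days early | After Week 1 end |
|---|---|---|---|---|
| 28 days | -13.2 | -29 to +4 | 49% | 0% |
| 30 days | -11.2 | -27 to +6 | 42% | 0.5% |
| 35 days | -6.2 | -22 to +11 | 26% | 15% |

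With 4-day weeks every error is one day earlier. Example: a 5-day Week 2 ending 26/FEB/2019 began on 22/FEB/2019. Counting back 30 days gives 23/JAN/2019, but the rule gives 01/JAN/2019, 22 days earlier.

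**Against the windows.** 14/84 = 17%, 16/84 = 19% and 27/84 = 32% of the induction period; 14/60 = 23%, 16/60 = 27% and 27/60 = 45% of the baseline look-back.

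**Effect on the ARR.** Expected relapses moved across one boundary per affected patient = rate x shift / 365.25.

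- Rate 0.14: 0.14 x 14/365.25 = 0.005; 0.14 x 27/365.25 = 0.010.
- Assumed pre-treatment rate 1.0: 14/365.25 = 0.04; 27/365.25 = 0.07.
- If 5% or 20% of patients had a missing day (assumed), at rate 1.0 and the mean absolute shift: 0.05 x 7.6/365.25 = 0.001; 0.20 x 7.6/365.25 = 0.004. Both are small beside 0.072.

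**The case against.** The strongest reply is that the effect is small and partly handled already. The study is descriptive and tests no hypothesis. Initiation dates decide eligibility, and Protocol 9.4 has inconsistent or missing data queried, so partial start dates may be few. The note that SAP version 3.0 revised the partial-date rules does not say which rules changed, so it is no evidence of frequency. The Day 1-365 sensitivity analysis recovers relapses pushed into Days 1-83, though in Year 1 rather than Year -1. Adverse events outside the on-treatment period stay in the listings, flagged, and so do imputed dates. Adverse events with partial onset dates in the initiation month are largely tied to the initiation date. All of this stands, and it limits the severity. It does not protect fully dated early events in the TEAE tables or the choice of baseline, and the SAP plans neither a count of imputed index dates nor an analysis without them.

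A reader might infer more than the documents support:

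- That every window moves. The Year 2 EDSS assessment follows the Year 2 treatment start when there was one, its confirmation follows that assessment, and time to subsequent DMT runs from the last dose.
- That both rules disregard all other dates. The missing-month rule does use the month of Week 2.
- That both rules commonly place the index after Week 1. At spacings of 28-30 days the missing-month rule does so in under 1% of dates.
- That the two rules pull in opposite directions. The 15th is nearly centred; only the missing-month rule leans one way, early.

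The 33-36% also describes all patients with a missing day. Recorded dates can correct only those who have them.

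**Conclusion.** The point holds as a minor defect. As written, the rules can produce an index date that contradicts recorded dosing dates. With a missing day the error runs from 14 days late to 16 days early, and about a third of evenly spread true starts get an index after Week 1 has ended. With a missing month the index is usually early, by about 11 days on average and up to 27 at 30-day spacing with 5-day weeks. These figures rest on evenly spread starts and the assumed week lengths and spacings. Because the number of partial start dates is not stated, the total effect cannot be computed. On the ARR it is probably small unless partial dates are common. The firmer reason to act is the misclassification of individual adverse events and baseline values.

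**What to change.** Amend SAP 9.10 (Dates of cladribine, start date):

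1. Keep the 15th as the default for a missing day, but never let an imputed start fall after a recorded Week 1 end date or before 22 August 2017.
2. Where the Week 1 end date is complete, derive the start from it and the week length, keeping the result within the recorded month. Use recorded treatment days if they exist, otherwise the usual 4 or 5 days. For a completed week of consecutive days, the error is then at most about 1 day.
3. Where day and month are missing and the Week 2 date is complete, count back about one month from that date instead of taking the 1st of the preceding month. State the interval in advance; any fixed choice near one month is a convention.
4. Report how many index dates were imputed and by which rule, and repeat the ARR without those patients.

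The cost is a few lines of SAP text and programming and one extra ARR run. No new data are needed if week-level dates are in the database. The existing rule already relies on a Week 2 end date; the documents do not show whether treatment days per week are recorded, so item 2 needs the fallback.
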